2. Demonstrate modulation of neurophysiological aftereffects of PPC stimulation by manipulating behavioral state. Based on preliminary data, our working hypothesis is that motor excitability will increase after PPC stimulation and will increase even more after stimulation during grasp performance.
3. Assess the relationship between brain connectivity, plasticity and behavior in response to the behavioral state during brain stimulation. Our working hypothesis is that constraining the behavioral state during PPC stimulation will induce greater changes in functionally specific parietal-motor pathways within the targeted cortical grasping network, as compared to PPC stimulation alone. Exploratory analyses will examine correlations between changes in action performance, plasticity, and functional connectivity.

RESEARCH DESIGN:

Participants will be asked to participate in up to nine sessions – the sessions will take place in either the TMS laboratory in the Kinesiology Building ([name]) or the Functional MRI Laboratory located in the Bonisteel building ([name]). The visit schedule is as follows:

- Session 1: Screening + behavioral & neurophysiological measures (~2 hours)
- Session 2: fMRI (~1 hour)
- Session 3: TMS (~30 min)
- Session 4: TMS (~30 min)
- Session 5: TMS (~30 min)
- Session 6: TMS + behavioral & neurophysiological measures (~3 hours)
- Session 7: TMS + fMRI (~1 hour)
- Session 8*: fMRI (~1 hour)
- Session 9*: behavioral & neurophysiological measures (~1 hours)

*Option to complete visits 8 and 9 on the same day

Subjects will be randomly assigned to one of three rTMS intervention groups in a 1:1:1 ratio. As depicted in **Figure 1**, subjects will complete fMRI scans, electrophysiological measures with TMS, and behavioral measures before and after five consecutive rTMS sessions. The first fMRI assessment session on visit 2, without rTMS, will obtain baseline measurements of hand motor function, electrophysiology with TMS, and fMRI-derived connectivity (providing the PPC target

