for iTBS – see below). The five consecutive rTMS sessions will provide the experimental manipulation. One rTMS intervention will apply iTBS to the PPC, while subjects concurrently perform a grasp task (iTBS PPC + Grasp). Another rTMS intervention will apply iTBS to the PPC, while subjects are in an unconstrained, resting state (iTBS PPC alone). This will allow us to elucidate the effects of targeted rTMS enhancement of the parietal-frontal grasping network and motor function, and the interaction between parietal iTBS and behavioral state. To test the functional specificity of stimulation to the PPC, a third rTMS intervention will apply iTBS to a cortical region outside of the cortical grasping network (vertex)¹ while subjects concurrently perform the grasp task (iTBS Vertex + Grasp). This condition can control for the strong somatic sensations of receiving the iTBS, which neither sham nor 45-degree tilt of the rTMS coil protocols can achieve.² There is also evidence that the 45-degree tilt excites neural tissue.³ This multimodal approach will allow us to visualize circuit-level modulation of the cortical grasping network related to targeted brain stimulation and motor behavior. Importantly, our pilot experiment shows that the average time from the end of rTMS to the beginning of the first post-rTMS fMRI is ~5 min, and that the fMRI assessment on visit 7 will be completed within 60 min. Findings from other groups⁴, as well as our own data, demonstrate that the effects of iTBS last for 60 min, data acquisition will occur in the appropriate time frame to capture the immediate iTBS-induced effects on the proposed brain and behavior outcomes. We also will perform a second post-rTMS assessment approximately 7-15 days after stimulation to estimate more lasting effects of stimulation on brain and behavior.

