The objective of Aim 2 is to determine inter-cortical interactions from PPC to motor plasticity. Descriptive statistics will be used to explore the distribution, central tendency, and variation of each measurement. Normality for each variable will be checked using a Shapiro-Wilks test, and appropriate transformations (i.e., log) will be used when necessary. To examine state-dependency modulation of rTMS-induced effects on motor plasticity, we will contrast the size of MEPs elicited in the resting hand muscle by TMS over M1 following iTBS PPC + Grasp with those following iTBS PPC alone. We will test the following: the size of MEPs evoked by TMS will be greater for iTBS PPC alone relative to iTBS Vertex + Grasp, and whether the MEPs will be greater for iTBS PPC + Grasp, compared to iTBS PPC alone. Because the MEP amplitude can be highly variable from trial-to-trial within the same subject,²⁸ we will collect 24 MEPs, the optimal number of single-pulse TMS trials required for the reliable assessment of motor cortical excitability.^{29,30} In addition, to avoid the confounding influence of diurnal variations in levels of cortisol on the induction of cortical plasticity,³¹ all experiments will occur at the same time of day. Based on prior work,³² it is possible that subjects with more excitable motor systems will have greater behavioral improvements after rTMS. We, will therefore perform additional analyses examining the relations of inter-individual differences in MEP amplitude, magnitude of the plasticity effects in the motor system,³³ and the rTMS-induced behavioral effects.³⁴ Knowledge of this variability will provide insight into how interventions can be personalized and optimized for stroke recovery.

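### As the visit list stands, the immediate post-intervention 9-HPT and MEP (primary outcomes 1 and 2) can come only from session 6, the fourth of five rTMS sessions, whereas the immediate fMRI outcomes follow the fifth; schedule and outcome time frames need reconciling

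*Combined protocol and SAP*

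**What the plan says.** All references are to the combined protocol and SAP.

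- **Visit list (Research Design).** TMS is listed at sessions 3, 4, 5, 6 and 7. Behavioral and neurophysiological measures appear at session 1 with screening, then at "Session 6: TMS + behavioral & neurophysiological measures (~3 hours"), then at "Session 9*: behavioral & neurophysiological measures (~1 hours"). The fifth TMS visit is listed as "Session 7: TMS + fMRI (~1 hour").
- **Design prose.** Participants have fMRI, "electrophysiological measures with TMS, and behavioral measures before and after five consecutive rTMS sessions". The five rTMS sessions together are described as the experimental manipulation. The later visit is introduced with "We also will perform a second post-rTMS assessment approximately 7-15 days after stimulation".
- **Outcome measures.** All four primary outcomes carry the same time frame, baseline to immediate post-intervention. So do secondary outcomes 5, 7, 9 and 11.
- **Measurements.** Cross-references tie the behavioral measures to primary 1 and secondary 1 and 7-10, the neurophysiological measures to primary 2 and secondary 2, 11 and 12, and the fMRI measures to primary 3-4 and secondary 3-6. The choice reaction task is done after each 9-HPT session.

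**The concern.** The outcome section gives 9-HPT, MEP and both fMRI primaries one common time frame. Read with the visit list, that time frame falls at two different points of the stimulation course. Staff who follow the list would measure two of the four primary outcomes before the last rTMS session, and the report would then present those values as post-intervention. The stake is interpretation: a mid-course measurement could be described as the effect of the full five sessions. There is also a smaller matter for Aim 3. If an exploratory correlation used immediate-post values, 9-HPT or MEP from one visit would be paired with connectivity from the next.

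**Working it through.** **Step 1: reproduce the plan's count.** TMS at sessions 3, 4, 5, 6, 7 gives 5, which matches the stated five rTMS sessions. The 3-minute iTBS trial run at the initial assessment is a tolerance check and is not counted.

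**Step 2: place each assessment visit in the course.**

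| Visit | Listed assessment | rTMS sessions completed before that day's | Including that day's |
|---|---|---|---|
| 1 | behavioral, neurophysiological | 0 | 0 |
| 2 | fMRI | 0 | 0 |
| 6 | behavioral, neurophysiological | 3 | 4 |
| 7 | fMRI | 4 | 5 |
| 8 | fMRI | 5 | 5 |
| 9 | behavioral, neurophysiological | 5 | 5 |

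With session 1 as baseline and session 9 as the 7-15 day follow-up, only session 6 is left for the immediate behavioral and neurophysiological values.

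**Step 3: exposure at that visit.** Each iTBS session delivers 600 pulses (rTMS Sessions; NIBS interventions).

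- Full course: 5 × 600 = 3,000.
- Session 6, measured after that day's iTBS: 4 × 600 = 2,400; 2,400/3,000 = 80%.
- Session 6, measured before that day's iTBS: 3 × 600 = 1,800; 1,800/3,000 = 60%.
- Visit 7 fMRI, which the prose places after rTMS: 3,000/3,000 = 100%.

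Aim 2 contrasts MEPs elicited "by TMS over M1 following iTBS PPC + Grasp with those following iTBS PPC alone", which makes the 80% case the more natural one, but it does not fix the order within session 6.

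**Step 4: outcomes affected.** There are 4 + 12 = 16 outcomes. Immediate-post: primary 1-4 and secondary 5, 7, 9, 11 = 8. Of these, fMRI outcomes are primary 3, 4 and secondary 5 = 3, which leaves 8 − 3 = 5 behavioral or neurophysiological. Secondary 7 is the force-tracking task, which is performed in the scanner and so can be obtained at visit 7: 5 − 1 = 4. The affected outcomes are primary 1 and 2 and secondary 9 and 11, that is 2 of 4 primary and 2 of 4 immediate-post secondary outcomes. The 8 follow-up outcomes are not affected.

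**Step 5: could the labels be incomplete?**

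- For: session 2 is listed as fMRI only, yet the prose says "The first fMRI assessment session on visit 2, without rTMS, will obtain baseline measurements of hand motor function, electrophysiology with TMS". The visit 7 timing is said "to capture the immediate iTBS-induced effects on the proposed brain and behavior outcomes", although behavior there could mean the force-tracking task alone. Calling the later visit a second assessment suggests a single first one.
- Against: session 7 is listed at about 1 hour, the same as scan-only sessions 2 and 8, and already includes iTBS. The functional runs alone take 6 × 5 = 30 minutes, with anatomical images on top. The behavioral and neurophysiological battery has about 1 hour to itself at session 9. No sentence places 9-HPT or MEP at session 7.
- Neither side settles it. The duration argument applies equally to session 2, where the prose does add measures, and Figure 1 is not available in the text reviewed.

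**The case against.** The best defence is that the split is deliberate. The Research Design section says iTBS effects last 60 minutes, the scan begins about 5 minutes after rTMS and the visit 7 fMRI is finished within 60 minutes. The sessions are held in two buildings. A peg test, three runs of the reaction task, 24 MEPs and dual-site TMS would be hard to fit into the same window, so using the last two rTMS visits for the two batteries is reasonable. Moreover, the term immediate post-intervention is never defined, and a value taken soon after iTBS at session 6 is immediate in the sense of that 60-minute window.

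The rationale stands as an explanation of the schedule. It does not cure the label: the same time frame is attached to outcomes that, as listed, fall at different points of a manipulation described as five sessions. If the split is intended, the outcome definitions should say so.

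Other points on that side stand in full. The list gives no within-visit order, so exposure is a range of 60% to 80%. The exploratory correlations have no stated time point, so the mismatch arises only if immediate-post values are used; at sessions 8 and 9 all five sessions have been given. And adding the measures to session 7 would have to be squared with the visit length and the scan window.

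A reader might also infer more than the documents support:

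- *That the treatment comparison is biased or power is lost.* All arms share the schedule, so the between-arm contrasts, type I error and sample size are untouched. Nothing in the documents shows that four sessions and five give different effects.
- *That the before-and-after sentence and the five-day wording of Aim 1 are contradicted.* They are not: session 9 comes after all five sessions, and Aim 1 does not say immediate.
- *That 9-HPT and MEP certainly will not be measured after the fifth session.* The evidence in step 5 leaves that open.

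**Conclusion.** Wrong as written; minor to moderate. The visit list and the outcome time frames do not agree for 2 of 4 primary outcomes and for secondary outcomes 9 and 11. As listed, these follow 3 or 4 of the 5 rTMS sessions (60% or 80% of pulses), against 5 of 5 for the immediate fMRI outcomes. This rests on taking the visit list at face value and on reading the intervention as the five sessions together, which is the natural reading but not a stated definition. If the measures are also taken at session 7 after iTBS, values after the full course exist; the schedule line would then be wrong and the plan would still have to say which visit's values are primary. No effect-size consequence is claimed. The consequence is confined to what the immediate result can be said to show.

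**What to change.** Reconcile the visit list with the outcome time frames, leaving every stimulation session as it is.

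- **If session 6 is the intended assessment:** restate the time frame of primary 1-2 and secondary 9 and 11 as session 6, the fourth of five rTMS sessions; state whether the measures precede or follow that day's iTBS; and do not describe the immediate result as the effect of the full five sessions. If any Aim 3 correlation uses immediate-post values, note that 9-HPT and MEP come from a different session than connectivity.
- **If these measures are in fact also taken at session 7:** correct the session 7 line, reconcile it with the listed duration of about 1 hour and with the 60-minute fMRI window, and state which session's values define the primary outcomes.

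Cost: the first option is wording only, namely four time frames, a statement of order, a sentence on interpretation and, if needed, one in Aim 3. Its downside is that the immediate primary result is described as a partial-course effect, a slightly less favourable claim. The second option also requires checking the session 7 duration and the scan-window statement. Neither adds a visit, a participant or a stimulation session.

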Subjects and Screening: To ensure experimental rigor, all research staff will be trained in Good Laboratory Practices, including standardized operating procedures and record keeping. We will recruit ~65 healthy subjects (50% women), ages 18-50, to allow for drop-outs and subjects who cannot tolerate iTBS. Subjects will be screened with the Transcranial Magnetic Stimulation Adult Safety Screen^{5,6,7} form in order to exclude subjects with contraindications for TMS and MRI, such as: a previous adverse reaction to TMS, a history of seizures or a condition that would increase the likelihood for seizures, a family history of epilepsy, taking medications that would increase the risk of seizure, pregnant or trying to become pregnant, presence of metal in the head (other than in the mouth), claustrophobia, presence of an implanted device like a pacemaker, metal in the brain, or other brain injuries or brain-related conditions.

Initial Assessment Session (screening): Subjects will watch a demo video of the 9-hole pegboard dexterity test (9-HPT, described below) from the NIH Toolbox for Assessment of Neurological and Behavioral function⁸ (www.nihtoolbox.org) in order to standardize instructions and familiarize subjects with the task. Subjects then will practice on the 9-HPT to reduce subsequent practice effects across sessions. Subjects will also practice Choice Reaction Task and Precision Force Task, both tasks are described below. The last step in the initial assessment session will be exposing subjects to TMS, beginning with motor threshold determination, followed by an assessment of the targeted functional parietal-motor pathway for the grasp task using a dual-site TMS method described below, and then a 3-min trial run of iTBS to the PPC target. In our experience, ~10-15% of subjects cannot tolerate iTBS, so this will eliminate those subjects without having wasted an expensive fMRI session.

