rTMS Sessions: Because multiple consecutive days of stimulation have been shown to produce longer-lasting effects on brain and behavior, 68,76-81 subjects will receive five consecutive rTMS sessions within a two-week period. A MagPro X100 magnetic stimulator with a 90mm figure-8 coil (MC-B70, MagVenture Inc.) will be used to apply rTMS to targeted locations marked on the structural MRI using a frameless infrared stereotactic neuronavigation system (Brainsight, Rogue Research, Montreal CA). Active motor threshold (AMT) will be obtained as the percentage of stimulator output that elicits a motor-evoked potential (MEP) of $\geq 200 \mu\text{V}$ peak-to-peak amplitude on 5 out of 10 trials while the subject maintains a 20% maximum contraction of the first dorsal interosseous (FDI) muscle of the right hand.^{9,10} We then will deliver iTBS to PPC or vertex,^{4,11} using 3 pulses of stimulation at 50 Hz, repeated every 200 ms, for 2s trains, repeated every 10s, for a total of 600 pulses in 190-s. Stimulation will be delivered at 80% of AMT, within consensus recommendations for safety.¹²

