We will determine an individualized left PPC stimulation location based on peak functional connectivity with the left motor cortex seed obtained at the baseline assessment on visit 1 using functional neuroimaging. This will account for individual variability in recruitment of the cortical grasping network and maximize the reliability of the rTMS-induced modulation. We will use those coordinates as the site of stimulation for the PPC target. The stimulation targets will be transformed from MNI space into each subject's original MRI space for anatomically guided TMS. We then will use a robust dual-site TMS 'hunting' procedure, recently developed by my laboratory, to determine the optimal PPC scalp location where TMS can effectively exert a grasp-specific facilitation of motor cortex on an object-driven grasp task inspired by previous work from both our group^{13,14,15} and others.^{16,17,18,19,20} For the vertex (control) target, we will locate the vertex according to the standard 10-20 system. We then will confirm using individualized fMRI from the baseline assessment session that the underlying cortical site is outside the functionally defined regions of interest for the targeted cortical grasp network, and adjust the coil on the scalp accordingly. We will use neuronavigation to enable reproducible placement of the TMS coil over the cortical targets for the multiple rTMS sessions. For the PPC stimulation alone intervention group, subjects will be instructed to maintain gaze on a fixation LED during stimulation. For vertex and PPC stimulation augmented with a task sessions, subjects will perform an object-driven grasping task.^{13,14,16,,21-26} Subjects will maintain fixation on a central LED in the midline (preview phase) for ~ 2 s. The illumination of an LED (green or red) then will instruct the subject to plan a precision grip towards either a small or large target object positioned in front of them. After 1 s, the LED will extinguish and cue subjects to execute the intended object-directed hand action. The presentation of the visual stimuli will be synchronized with the iTBS stimulation, which will occur 800 ms before the onset of every 'GO' cue in order to modulate cortical activity during both the planning and execution phase of the action.

Detailed objectives:

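### Three arms cannot isolate the interaction between PPC stimulation and behavioral state: PPC + Grasp versus PPC alone also carries the effect of the grasp task itself

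*Combined protocol and SAP*

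**What the plan says.** Research Design randomises participants 1:1:1 to PPC + Grasp (PG below), PPC alone (PA) and Vertex + Grasp (VG). Its stated purpose includes learning about "the parietal-frontal grasping network and motor function, and the interaction between parietal iTBS and behavioral state".

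The arms differ in what participants do during stimulation:

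- PA: "Another rTMS intervention will apply iTBS to the PPC, while subjects are in an unconstrained, resting state (iTBS PPC alone". The rTMS Sessions section adds: "For the PPC stimulation alone intervention group, subjects will be instructed to maintain gaze on a fixation LED during stimulation".
- PG and VG: "For vertex and PPC stimulation augmented with a task sessions, subjects will perform an object-driven grasping task".

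The dose is three-pulse bursts at 50 Hz, "repeated every 200 ms, for 2s trains, repeated every 10s, for a total of 600 pulses in 190-s", with stimulation tied to every GO cue. The schedule lists "Session 6: TMS + behavioral & neurophysiological measures (~3 hours") and then "Session 7: TMS + fMRI (~1 hour"), so on the schedule the post-intervention 9-HPT and MEP fall at the fourth rTMS visit.

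Under Detailed objectives, Aims 1 and 2 name two contrasts for the 9-HPT and MEP: PA versus VG, and PG versus PA. Aim 2 presents PG versus PA as the test of state-dependent modulation. Aim 3 contrasts PG with both other arms, but only for connectivity.

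**The concern.** An interaction between stimulation site and task needs all four combinations of the two factors. The plan has three; vertex stimulation without the task is missing. PG and PA differ in whether the brain was in a grasping state during PPC stimulation, and also in whether the right hand made repeated precision grips. The outcomes are manual dexterity and motor excitability of the hand, which such grips might change whatever site is stimulated.

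At stake is the mechanism claim. A PG advantage over PA would be reported as state-dependent stimulation when it could be practice, or task-related excitability, added to an ordinary PPC effect. The contrast that holds the task constant, PG versus VG, is not named for the 9-HPT or MEP.

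**Working it through.** **Planned size.** The Statistical Design section requires 54 participants for an η² of 0.11, alpha 0.05 and power 0.8. With f² = 0.11/0.89 = 0.1236, this figure is reproduced (power 0.804) as a group-by-time interaction with 3 groups and 3 time points and G*Power's SPSS-type effect size: λ = 0.1236 × (54 − 3) × 2 = 12.6, df 4 and 102. The plan does not name this variant. Here the figure only supplies n = 54/3 = 18 per arm.

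**Grip count.** One train is 10 bursts × 3 pulses = 30 pulses, and 600/30 = 20 trains per session. Assuming one GO cue per train, there are 20 grips per session. rTMS is given at Sessions 3 to 7.

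- Up to the Session 6 9-HPT and MEP: 4 × 20 = 80 grips in PG and VG, 0 in PA.
- Up to the Session 7 fMRI and the follow-up: 5 × 20 = 100 against 0.

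These come on top of hand-task exposure common to all arms: the peg test, force tracking, and at screening "an assessment of the targeted functional parietal-motor pathway for the grasp task using a dual-site TMS method".

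**Identifiability.** Take vertex iTBS without the task as reference. Let s be the PPC-versus-vertex effect without the task, p the grasp-task effect under vertex iTBS, and i the interaction. The arm means are VG = p, PA = s and PG = s + p + i, so:

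- PG − PA = p + i
- PA − VG = s − p
- PG − VG = s + i

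The third line is the sum of the first two. That leaves two independent equations for three unknowns. Equivalently, the design matrix for intercept, site, task and site × task has rank 3 for four parameters. Hence i is not estimable at any n.

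**Two scenarios the trial cannot tell apart (SD units).**

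| Scenario | s | p | i | PG − PA | PA − VG |
|---|---|---|---|---|---|
| No state-dependence | 1.0 | 0.5 | 0 | 0.5 | 0.5 |
| State-dependence | 0.5 | 0 | 0.5 | 0.5 | 0.5 |

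**Illustrative size.** The documents give no value for p, so a range is assumed. With 18 per arm, pooled SD and df = 51, the noncentrality is d × √(18/2) = 3d. With i = 0, PG − PA equals p, and the chance that PG is significantly better (two-sided 0.05, upper tail) is:

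| p (SD) | 0 | 0.2 | 0.3 | 0.5 | 0.8 |
|---|---|---|---|---|---|
| PG > PA significant | 2.5% | 8.5% | 14% | 31% | 65% |

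The same p lowers PA − VG. The chance that both predicted contrasts are significant (2,000,000 simulated trials) is:

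| s, p, i | Both significant |
|---|---|
| s = p = 0.2, 0.3, 0.5, 0.8; i = 0 | 0.01%, 0.02%, 0.1%, 0.6% |
| 1.0, 0.5, 0 | 4.4% |
| 0.5, 0, 0.5 | 4.4% |
| 1.6, 0.8, 0 | 37% |
| 0.8, 0, 0.8 | 37% |

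Scenarios with and without an interaction give the same rate whenever their arm differences match.

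**The case against.** The best reply is that the plan prespecifies no factorial interaction test. Aims 1 and 2 ask whether results are better still when PPC stimulation is given during grasp, and PG versus PA is a valid randomised answer to whether adding the task helps. The word interaction could be meant loosely. This stands in part: the contrast is sound for the combined package. But the stated purpose goes further, and Aim 2 attaches the state-dependency label to that contrast.

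Second, p may be small. Participants are healthy and practise the 9-HPT beforehand to limit practice effects. All arms share other hand tasks. One peg-test run has 9 placements and 9 removals, so 80 grips amount to about 80/18 = 4.4 runs. This is fair, and it limits what can be said about size. Shared exposure does not, however, balance grips made in only two arms.

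Third, p works against PA versus VG, so the full predicted pattern is rarely produced by a task effect alone. It reaches 37% only at s = 1.6 SD. Reading the planning η² as a between-arm effect with evenly spaced means (an assumption), PG − VG would be 0.352 × √6 = 0.86 SD, about half of that. This is true, but genuine state-dependence with the same arm differences gives the same low rates, so seeing the pattern does not discriminate.

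Fourth, the grip count is inferred, and Research Design also describes measures before and after five rTMS sessions, which would make it 100. The argument does not depend on the count.

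Finally, PG versus VG estimates s + i and does not isolate i either. Correct: the remedy narrows the claim and does not rescue it.

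**Conclusion.** The concern holds. The design cannot deliver the interaction that Research Design promises, and PG versus PA for the 9-HPT and MEP supports only a statement about grasp practice together with stimulation during grasp. That conclusion is exact and assumes no effect size.

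How far the published conclusion could mislead depends on the grasp-task effect, which the documents do not give. The 8.5% to 65% range is an illustration over an assumed 0.2 to 0.8 SD with no interaction. The 80-against-0 count rests on one cue per train and on the visit schedule. The trial remains useful and its randomised contrasts remain valid. The interpretation should be narrowed before analysis.

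**What to change.** 1. Prespecify PG versus VG for the 9-HPT and MEP, as Aim 3 already does for connectivity. It is the practice-matched test of PPC stimulation during grasp, and the Aim 1 model can supply it. With 18 per arm it has 84% power for 1.0 SD and 80% power at 0.95 SD.
2. Report PG versus PA as the combined effect of grasp practice and stimulation during grasp.
3. Report the VG change from baseline as indirect evidence on the task effect, stating that this assumes inert vertex iTBS and small retest effects. Its 95% half-width is about 2.008/√18 = 0.47 SD, so it bounds the effect only roughly.
4. Remove the interaction claim from Research Design and the state-dependency label from Aim 2.

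The cost is a narrower claim, with no extra participants, visits or measurements.

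Giving PA matched grips well separated from iTBS is an option for the investigators to weigh. It is not a required change, because grips close to stimulation could alter the resting state that arm is meant to have.

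A fourth arm is not proposed. The interaction contrast would have standard error √(4/18) = 0.47 SD at 18 per arm, so 80% power needs about 1.3 SD. Detecting 0.8 SD would take about 50 per arm, or 200 completers.
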